### **8.2 Statistical Analysis Plan and Sample Size Determination**

Determination of overall response rate will be calculated based on the evaluable population of patients who received at least 1 dose of therapy. Best overall response at any time will be compared in the study population to benchmark values in the literature. Overall and progression free survival will be determined according to the method of Kaplan and Meier and analyzed for each cohort. For the endpoints of ORR, OS and PFS, each of these will be analyzed in groupings of patients according to biomarkers of interest including (a) PD-L1 expression on archival tissue and current peripheral blood CTCs, (b) peripheral blood T cell subset analysis, (c) quantitative T-cell tumor infiltration, and (d) genomic complexity and (e) integrin expression pattern in tumor blood vessels. The impact of treatment on the levels of PD-L1 expression, T-cell subsets and Tumor infiltrating lymphocytes will be compared in archival and post treatment biopsy specimens. Adverse events will be tabulated for the duration of the trial and reported in tabular format.

Sample size is determined independently for each of the 2 patient groups, and is based on overall response rate using a Simon Optimal 2-stage design.

$$H_0: \pi < 20\%$$

$$H_a: \pi > 45\%$$

where  $\pi$  = the true response rate (same rate used for NSCLC and H&N Cancer)

For the type 1 and type 2 error probability,  $\alpha=\beta=0.10$ , up to 25 patients are required in each arm to have sufficient power to test the hypothesis. Interim response rate will be determined after 14 patients have been enrolled on each arm. If there are fewer than 3 responses in the first 14 patients, the alternate hypothesis will be rejected and that arm of the study will be closed. If 4 or more responses occur, then accrual will continue on that arm until 25 patients have been treated and evaluated. If 8 or more of the 25 patients experience an objective response, then we will conclude that the true response rate is clearly greater than 20% and not incompatible with a response rate of 45% - and this will serve as a signal indicating that the

two drugs together are better than either alone. However, if 7 or fewer patients experience a response, then we will conclude that the true response rate is less than 45% and not incompatible with a response rate of 20%.

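### The interim rule gives no decision at exactly 3 responses in 14, and its stop limit is one lower than that of the Simon optimal design it names

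*Combined protocol and SAP*

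**What the plan says.** Section 8.2 states that the sample size "is based on overall response rate using a Simon Optimal 2-stage design". It tests a response rate of 20% against 45% in each cohort, with both error rates at 0.10 and up to 25 patients per cohort.

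The decision rules in the same paragraph are:

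- **Timing of the interim:** "Interim response rate will be determined after 14 patients have been enrolled on each arm".
- **Stop:** "If there are fewer than 3 responses in the first 14 patients, the alternate hypothesis will be rejected", and the arm is closed.
- **Continue:** "If 4 or more responses occur, then accrual will continue on that arm until 25 patients have been treated and evaluated".
- **Final success:** "If 8 or more of the 25 patients experience an objective response", the rate is taken to exceed 20%.
- **Final failure:** seven or fewer responses.

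The rest of Section 8.2 adds that up to four more patients may be accrued while the first 14 are assessed. Sections 2.1 and 5.1.1 note that the NSCLC cohort closed as of the July 2018 interim analysis, without giving a response count. Section 10.2.5.2.3 assigns interim efficacy and futility analyses to the DSMC, without a threshold. None of these says what happens at 3 of 14.

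**The concern.** The stop sentence covers 0, 1 and 2 responses and the continue sentence covers 4 and above. The value between them is assigned to neither. The limit of fewer than 3 also looks wrong for the named design: if stopping is confined to 2 or fewer and everything else is kept, the type I error passes 0.10.

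Response rate is the primary endpoint, and this is the only response-based stopping rule. Section 5.8 lists data quality, adherence, safety and drug development as grounds for termination, and the toxicity rule in Section 8.2 concerns tolerability. The unassigned result is one of the likelier ones if the combination adds nothing. In an open-label trial the choice would then be made with the responses already known. If the choice is to continue, up to 11 more patients enter a cohort that the named design would have closed.

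**Working it through.** **Inputs (all Section 8.2).** p0 = 0.20, p1 = 0.45, alpha = beta = 0.10, n1 = 14, N = 25, success at 8 or more of 25.

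**Step 1: reproduce the plan's design.** An exact binomial search over two-stage designs with N up to 40, requiring alpha ≤ 0.10 and power ≥ 0.90 and minimising expected N at p0, returns:

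- stop at 3 or fewer of 14, continue at 4 or more, success at 8 or more of 25.

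The next-best design (stop at 2 or fewer of 12, then 25) has expected N 17.74 against 17.32. The plan's 14, 25, 8 and its continue limit of 4 or more are therefore exactly those of the optimal design. Among designs with n1 = 14 and N = 25, this is the only one that meets both error limits. The minimax design is different (stop at 3 or fewer of 15, success at 8 or more of 24). None of the other alpha, beta or p1 values tried gave a limit of 2 of 14 with 25 patients.

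**Step 2: probability of the unassigned result.** P(X = 3) = C(14,3) p³(1 − p)¹¹, with C(14,3) = 364.

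- p = 0.20: 364 × 0.008 × 0.0859 = 0.250
- p = 0.25 (the single-agent SCCHN rate cited in Section 4.2.1): 364 × 0.015625 × 0.04224 = 0.240
- p = 0.45: 364 × 0.091125 × 0.001393 = 0.046

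**Step 3: operating characteristics under the two ways of resolving 3 of 14.** With stop limit r1,

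P(success) = Σ over x > r1 of P(X1 = x) × P(X2 ≥ 8 − x), where X1 ~ Bin(14, p) and X2 ~ Bin(11, p).

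At p = 0.20 with r1 = 3, the terms for x = 4, 5, 6, 7 and 8 or more are 0.0277 + 0.0329 + 0.0219 + 0.0084 + 0.0024 = 0.0933.

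If 3 of 14 continues (r1 = 2), one term is added:

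- p = 0.20: 0.2501 × P(X2 ≥ 5) = 0.2501 × 0.0504 = 0.0126, so alpha = 0.0933 + 0.0126 = 0.1059.
- p = 0.45: 0.0462 × 0.6029 = 0.0279, so power = 0.9026 + 0.0279 = 0.9305.

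Early stopping at p0 is P(X1 ≤ 3) = 0.698 or P(X1 ≤ 2) = 0.448. Expected N is 14 + 11 × (1 − early-stop probability):

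- 14 + 11 × 0.302 = 17.3
- 14 + 11 × 0.552 = 20.1

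| | 3 of 14 stops | 3 of 14 continues |
|---|---|---|
| Type I error | 0.093 | 0.106 |
| Power | 0.903 | 0.931 |
| Early stop at 20% | 0.698 | 0.448 |
| Expected N at 20%, no overrun | 17.3 | 20.1 |
| Expected N at 20%, full overrun of 4 | 20.1 | 21.9 |

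The last row takes 18 patients treated whenever the cohort stops: 18 + 7 × 0.302 = 20.1 and 18 + 7 × 0.552 = 21.9.

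**Step 4: what continuing from 3 of 14 offers.** Such a cohort needs 5 or more responses in the next 11 patients. At a true rate of 20% the chance of that is 5.0%.

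**The case against.** Several points on the other side are fair.

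- **Type I error.** The excess is small, 0.106 against 0.10. It arises only if a 3-of-14 cohort continues, which the continue sentence does not authorise. Read together, the two sentences leave 3 undefined; they do not define a design with a limit of 2. Continuing would also raise power. This stands, and it puts the weight on the missing decision and the lost early stopping more than on alpha.
- **Expected sample size.** The permitted overrun of four patients narrows the difference from 2.75 patients to 1.75. This stands as a range; the direction is unchanged.
- **Scope.** The NSCLC cohort is already closed, so the rule can only act on the SCCHN cohort, and the documents do not say whether that cohort has passed its interim. This stands, but the version dated 06Aug2019 still carries the rule, and the stated error rates depend on it.
- **Who decides.** Interim reviews belong to an independent DSMC, so the choice is not the investigator's alone. The committee nevertheless has no threshold to apply at 3.
- **Which sentence is wrong.** That the stop sentence is the slip is an inference. It is well supported, because the other four figures (14, 25, 8 and the continue limit of 4) all match the optimal design.

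None of these supplies an action for 3 of 14 or makes fewer than 3 the limit of the named design.

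**Conclusion.** The concern holds. Section 8.2 leaves exactly 3 of 14 without a decision, and its stop limit is one below that of the Simon optimal design on which the plan relies. The gap is reached about one time in four per cohort if the true rate is 20%. If it is resolved by continuing, the chance of closing an inactive cohort early falls by 25 percentage points and the stated 0.10 type I error no longer holds, though by only 0.6 of a percentage point.

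These figures assume independent binary responses, exactly 14 and 25 evaluable patients, and a final test on 25. The documents do not show whether either cohort had exactly 3 responses, so any actual effect on the trial is unknown.

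**What to change.** In Section 8.2, change the stop limit from fewer than 3 to 3 or fewer responses in the first 14, and leave the continue limit of 4 or more as it is. State the exact properties beside the rule: alpha 0.093, power 0.903, probability of early stopping 0.70 at a 20% response rate.

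Because an interim analysis was held in July 2018, the amendment should also record, for each cohort whose interim has taken place, the response count and the limit that was applied. This shows whether the correction affects a decision already taken.

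The cost is a short text amendment. Sample size, final cut-off and trial procedures do not change.

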### Toxicity Stopping Rules

Unacceptable toxicity is defined as drug related CTCAE v4.0 toxicity of grade 3 or more that does not resolve within 12 weeks. Patients who are removed from the trial for unacceptable toxicity and have not yet been evaluable for response will be classified as non-responders. We anticipate a drug related discontinuation rate of 10%.

For the purpose of assessing tolerability on an on-going manner and to have criteria to lead to review of all safety and toxicity in order to consider modifying the starting dose of either sEphB4-HSA or Pembrolizumab or both, unacceptable toxicity (TOX) will be defined as the inability to continue treatment to a 3rd course. Each cohort, a) lung and b) head/neck will be evaluated separately for:

- any toxicity (at least possibly related to treatment) that lead to treatment discontinuation prior to the start of the 3rd course
- inability for immune related toxicities to resolve within 42 days, during the 1st two courses.

Criteria for flagging an excessive number of patients with TOX are based on the sequential probability ratio test with  $\alpha=0.10$ ,  $\beta=0.10$ ,  $p_0=0.10$  and  $p_a=0.30$ . Every time a patient is classified as having had a TOX, the cumulative number of patients (X) who have experienced a TOX will be compared to the number of patients (N) who were enrolled at the time that the patient who experienced TOX, was enrolled. If the number of patients, N, is greater than  $N_X$ , the number given in the bottom row of the Table below, then the boundary has not been crossed. If N is less than or equal to  $N_X$ , then the boundary has been crossed and a careful review of all the toxicities and tolerability will be initiated.

Table: Boundary for Monitoring Safety/Tolerability				
X: # pts who experienced a TOX	3	4	5	6
N X : Boundary crossed if # pts. at risk (N) is $\leq N_X$	$\leq 7$	$\leq 12$	$\leq 18$	$\leq 23$

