### **5.7 Subject Replacement Strategy**

Patients who are deemed not evaluable for response will be replaced

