Once 14 patients in each cohort have been enrolled, accrual to the study can continue for up to 4 additional patients while waiting for the first 14 patients to be evaluated. Patients will be considered evaluable for response if they are eligible for treatment, and receive 1 dose of therapy. Those patients who are deemed not evaluable will be replaced.

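### The toxicity boundary keeps early non-toxic leavers in N, so under the bulleted TOX definition they score as tolerating treatment and lower the chance of a review

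*Combined protocol and SAP*

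**What the plan says.** Under Toxicity Stopping Rules in section 8.2, the criteria "are based on the sequential probability ratio test with" alpha = beta = 0.10, p0 = 0.10 and pa = 0.30, applied to each cohort separately. Each time a patient is classified as a TOX, the running count X "will be compared to the number of patients (N) who were enrolled at the time that the patient who experienced TOX, was enrolled". The boundary table heads this same N differently: "Boundary crossed if # pts. at risk (N) is" at most 7, 12, 18 or 23 for X = 3, 4, 5 or 6. If it is met, "then the boundary has been crossed and a careful review of all the toxicities and tolerability will be initiated".

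TOX is described twice. The lead-in says "unacceptable toxicity (TOX) will be defined as the inability to continue treatment to a 3 rd course". The first bullet below it is narrower: "any toxicity (at least possibly related to treatment) that lead to treatment discontinuation prior to the start of the 3 rd course". The second bullet covers immune-related toxicity in the first two courses that does not resolve within 42 days.

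Evaluability and replacement are defined for response only. Section 8.2 has "Patients will be considered evaluable for response if they are eligible for treatment, and receive 1 dose of therapy", and section 5.7 has "Patients who are deemed not evaluable for response will be replaced". There is no evaluability rule for TOX.

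**The concern.** A sequential probability ratio test (SPRT) treats each of the N patients as a finished yes/no observation. Under the bullets, a patient has given such an observation only by having a TOX or by getting through two courses without one. A patient who leaves in that window through death, intercurrent illness or withdrawn consent has given neither. The rule nevertheless keeps that patient in N, where the test reads a non-TOX. Each such patient moves the cohort away from the boundary without having shown tolerability.

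A second, smaller fault is in the same sentence. X counts every TOX so far, but N is the position of the patient classified last. These match only if TOX patients are classified in enrolment order.

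At stake is the sensitivity of the protocol's one numerical tolerability trigger, at the rate the plan itself treats as excessive.

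**Working it through.** **Inputs.** From section 8.2: alpha = beta = 0.10, p0 = 0.10, pa = 0.30, limits 7/12/18/23 and a maximum of 25 patients per cohort. Assumed, because the documents do not give it: d, the share of patients who leave before course 3 for non-toxic reasons.

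**1. The plan's boundary.** The upper SPRT limit flags when X·ln(pa/p0) + (N − X)·ln[(1 − pa)/(1 − p0)] ≥ ln[(1 − beta)/alpha]. Solving for N:

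N_X = X + [X·ln 3 − ln 9] / ln(0.9/0.7) = X + [1.0986·X − 2.1972] / 0.2513

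- X = 3: 7.37, rounded down to 7
- X = 4: 12.74, to 12
- X = 5: 18.11, to 18
- X = 6: 23.49, to 23

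The printed table reproduces exactly, so the limits are not in question.

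**2. Flagging probability with no leavers.** Let F(p, n) be the chance of a flag among n patients taken in enrolment order, each a TOX with probability p. It comes from an exact recursion on the TOX count, flagging when the X-th TOX falls at position N_X or earlier. F(0.30, 25) = 78.9% and F(0.10, 25) = 5.7%.

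**3. Rule as written, with leavers.** A leaver occupies a position but cannot be a TOX, so the monitored rate becomes p(1 − d) and the flag chance is F(p(1 − d), 25). For p = 0.30 the effective rate is 0.285, 0.27 and 0.24 at d = 5%, 10% and 20%.

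**4. Leavers taken out of N and not replaced.** The number contributing, m, is binomial(25, 1 − d), and the flag chance is F(p, m) averaged over m.

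| d | p = 30%, as written | p = 30%, leavers out | p = 10%, as written | p = 10%, leavers out |
|---|---|---|---|---|
| 0 | 78.9% | 78.9% | 5.7% | 5.7% |
| 5% | 74.4% | 78.5% | 4.9% | 5.7% |
| 10% | 69.3% | 77.0% | 4.1% | 5.6% |
| 20% | 57.5% | 72.7% | 2.8% | 5.2% |

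At p = 30% the loss due to the definition of N is 78.5 − 74.4 = 4.1 points, 77.0 − 69.3 = 7.7 points and 72.7 − 57.5 = 15.2 points. The rest of the fall from 78.9% comes from having fewer than 25 informative patients.

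**5. Partial exposure.** If leavers carry half the TOX risk before they go, the as-written rate is p(1 − d) + d·p/2 = p(1 − d/2). For p = 0.30 this is 0.285 at d = 10% (flag chance 74.4%) and 0.27 at d = 20% (69.3%).

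**6. Order of classification.** Suppose patients 12 and 10 are classified before patient 3. At the third TOX the rule compares X = 3 with N = 3, and 3 ≤ 7 crosses. The data are 3 TOX among 12 enrolled, and 12 > 7 does not cross. Simulated at 25 patients per year with classification lags of up to 6 to 18 weeks, this moves false flags at a 10% TOX rate from about 5.7% to 6.3-7.6%.

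**The case against.** A reader might infer that the rule counts everyone enrolled. It does not: N stops at the TOX patient's own position, so later enrolments are already left out. In a calendar-time simulation (30% TOX, no leavers, 42-day window, 14.6 days per patient) the rule as written flags 80.0%; counting everyone enrolled at the time of the TOX would flag 72.8%. Nor does the text choose enrolled over at-risk patients. The table calls the same N at risk, and the fault is that no exclusion makes the two descriptions agree.

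Four further objections have weight.

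- **The lead-in.** Read literally, it makes any early leaver a TOX. Leavers would then add to X as well as N, and the bias would reverse. The dilution therefore depends on the bullets governing.
- **The meaning of 30%.** The plan does not say that pa is conditional on staying two courses. If it is a rate per enrolled patient, the table flags 78.9% and nothing is diluted.
- **The exit share.** Imaging is every two cycles (section 7.1.2.6), progression normally has to be confirmed (section 5.6), and entry requires ECOG 0 or 1 (section 5.1.2). Radiographic progression should seldom end treatment before course 3, which points to a low d. Never-dosed patients are also likely to be few, since section 7.1.1.6 ties the study ID to starting treatment.
- **The consequence.** Crossing starts a review, not a stop. Section 10.2.5.2.3 separately gives the Data and Safety Monitoring Committee real-time and quarterly safety monitoring. A missed flag does not mean that toxicity goes unreviewed.

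These points limit the size of the concern. They do not supply the missing rule: section 8.2 still leaves open how early non-toxic leavers count.

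**Conclusion.** The concern holds in this limited form. The boundary itself is correct, but the N compared with it includes patients who have not given the observation the test assumes. Under the bullets, and with 30% taken as the rate among patients who stay at risk, the avoidable loss of sensitivity is about 4 points at a 5% exit share, 8 at 10% and 15 at 20%. The lower end is more plausible, and partial exposure of leavers shrinks the loss further. The ordering fault works the other way, towards extra flags, and is minor: the simulated false-flag rates remain below the nominal 10%. The documents do not support saying that the rule divides by all enrolled patients or that an excessively toxic regimen would escape review. What is affected is the sensitivity of one review trigger.

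**What to change.** Amend the sentence in section 8.2 that defines N:

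- N is the number of patients, in enrolment order, up to and including the latest-enrolled patient with a TOX.
- Leave out only patients never dosed, or off treatment before course 3 for non-toxic reasons.
- Keep patients still in courses 1-2 in N. Limiting N to patients with a TOX or two completed courses would drop them and raise false flags to about 7%.
- Keep the printed N_X values.

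Reconcile the TOX lead-in with its bullets so that one definition applies. The exclusion above presumes that non-toxic exits are not TOX; if the sponsor intends the lead-in literally, those patients belong in both X and N.

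The cost is a short text change and slightly more reviews: about 5-6% of cohorts at a 10% TOX rate, against 2.8-4.9% as written at exit shares of 20% down to 5%, and below the nominal 10%. Removing leavers also discards their partial follow-up, so it slightly over-corrects if they carried some TOX risk before leaving. Section 2.1 records the lung cohort as closed, so for new enrolment the change bears on the head and neck cohort.

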## 9.0 LABELING, PACKAGING, STORAGE AND RETURN OF CLINICAL SUPPLIES

### 9.1 Investigational Product

The investigator shall take responsibility for and shall take all steps to maintain appropriate records and ensure appropriate supply, storage, handling, distribution and usage of investigational product in accordance with the protocol and any applicable laws and regulations.

Clinical Supplies will be provided by Merck and Vascene as summarized in Table 7.

Table 7 Product Descriptions

Product Name & Potency	Dosage Form
pembrolizumab 50 mg	Lyophilized Powder for Injection
pembrolizumab 100 mg/ 4mL	Solution for Injection
sEphB4-HSA 25 mg/mL	Solution in 10 mM L-Histidine, 150 mM Sodium Chloride, and 10% Sucrose, pH 7.0

### 9.2 Packaging and Labeling Information of sEphB4-HSA

The study drug will be packaged and labeled according to current Good Manufacturing Practices (GMP). Details of the packaging and labeling of clinical supplies may be found in the Pharmacy Manual. sEphB4-HSA is supplied in a single-use vial containing 10 mL (250mg) of sEphB4-HSA. Each vial contains a concentrated solution with the equivalent of 250 mg of sEphB4HSA (25 mg/mL).

Dose calculations for sEphB4-HSA will be on the basis of actual body weight at the start of each cycle.

- Allow the appropriate number of vials of sEphB4-HSA to stand at room temperature for approximately 15 minutes before preparation.
- Ensure that the sEphB4-HSA solution is a colorless, clear to slightly opalescent solution, essentially free of particles on visual inspection.
- Aseptically withdraw the required volume of sEphB4-HSA solution into a syringe, and dispense into an i.v. bag. (If multiple vials are needed for a subject, it is important to use a separate sterile syringe and needle for each vial to prevent problems such as dulling of needle tip, stopper coring, repeated friction of plunger against syringe barrel wall and so on).
- The total dose to be administered will be diluted to a total volume of 200 mL with sterile normal saline and placed in EVA mixing container (B.Braun Cat #2112389).

- Prepare the sEphB4-HSA solution for infusion per the example provided below: Total dose should be calculated as follows: Subject body weight in kg x 10 mg (for the 10 mg/kg dose) = total dose in mg; a subject with a body weight of 70 kg would be administered 700 mg of sEphB4-HSA (70 kg x 10.0 mg/kg = 700 mg). thirty two mL of sEphB4-HSA and 168 mL of normal saline would be mixed in the i.v. bag and the solution would be infused over 60 minutes.
- Mix by GENTLY inverting several times. DO NOT shake.
- Visually inspect the final solution. If the infusion is not clear or the contents appear to contain precipitate, the solution should be discarded and documented on the Drug Accountability Log.
- Record the time sEphB4-HSA was prepared on the i.v. bag label.
- Attach the i.v. bag containing the sEphB4-HSA solution to the Non- PVC tubing with infusion set, 0.2  $\mu$ m in-line filter, and infusion pump.
- The infusion rate of the infusion pump should be adjusted to allow for a total infusion time of 60 minutes.
- At the end of the infusion period, flush the line with a sufficient quantity of normal saline. Do not enter into each vial more than once. Do not prepare sEphB4-HSA for infusion in glass syringes. Do not administer study drug as an i.v. push or bolus injection.

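### The worked preparation example for sEphB4-HSA draws 32 mL for a 700 mg dose, but at the stated 25 mg/mL that volume holds 800 mg, 14.3% too much

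*Combined protocol and SAP*

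**What the plan says.** Section 5.2 (Table 2) sets sEphB4-HSA at 10 mg/kg by weekly infusion, on Days 1, 8 and 15 of each 3-week cycle. Section 9.2 describes how to prepare it.

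- **Vial.** "sEphB4-HSA is supplied in a single-use vial containing 10 mL (250mg) of sEphB4-HSA". The next sentence repeats the strength: "Each vial contains a concentrated solution with the equivalent of 250 mg of sEphB4HSA (25 mg/mL"). Table 7 in Section 9.1 agrees: "sEphB4-HSA 25 mg/mL".
- **Dose rule.** "Subject body weight in kg x 10 mg (for the 10 mg/kg dose) = total dose in mg".
- **Bag volume.** "The total dose to be administered will be diluted to a total volume of 200 mL with sterile normal saline".
- **Worked example.** "a subject with a body weight of 70 kg would be administered 700 mg of sEphB4-HSA", after which "thirty two mL of sEphB4-HSA and 168 mL of normal saline would be mixed in the i.v. bag".

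The bullet containing the example directs staff to prepare the infusion by following it. Nowhere else in the document is a dose in milligrams turned into a volume to draw.

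**The concern.** The example combines a dose, a concentration and a volume that do not agree with one another. The first two are stated clearly, and the concentration appears in two separate sections, so the volume is the figure that stands out.

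This matters because the text is a dosing instruction for the experimental drug. If staff take the 32 mL at face value for a 70 kg patient, or derive a volume per kilogram from it, the dose given departs from the dose that the protocol defines. Repeated at each weekly infusion, that would alter exposure, could add to the toxicity counts, and would mean that the response rate belongs to a regimen other than the stated one.

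The plan also lacks an obvious trap for such an error. The overdose definition in Section 7.2.1 covers pembrolizumab only. Section 5.4.2 treats hypertension as an expected effect of sEphB4-HSA, so an effect of over-preparation could be read as ordinary drug toxicity.

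**Working it through.** **Inputs**

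| Quantity | Value | Source |
|---|---|---|
| Body weight in the example | 70 kg | Section 9.2 |
| Dose per kg | 10 mg/kg | Section 9.2; Table 2 in Section 5.2 |
| Vial content | 250 mg in 10 mL | Section 9.2 |
| Concentration | 25 mg/mL | Section 9.2; Table 7 in Section 9.1 |
| Drug volume in the example | 32 mL | Section 9.2 |
| Saline in the example | 168 mL | Section 9.2 |
| Total bag volume | 200 mL | Section 9.2 |

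**What reproduces**

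- Dose: 70 kg × 10 mg/kg = 700 mg, as stated.
- Concentration: 250 mg / 10 mL = 25 mg/mL, as stated.
- Bag volume: 32 mL + 168 mL = 200 mL, as stated.

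**What does not reproduce**

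- Volume to draw = dose / concentration = 700 / 25 = 28 mL, against the stated 32 mL.
- Saline to reach 200 mL = 200 − 28 = 172 mL, against the stated 168 mL. The saline figure was balanced against the wrong drug volume, so both need to change.

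**What the 32 mL bag contains**

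- 32 mL × 25 mg/mL = 800 mg, which is 100 mg more than intended.
- 800 / 700 = 1.143, an excess of 14.3%.
- 800 mg / 70 kg = 11.43 mg/kg.
- Over the three infusions of a cycle: 3 × 11.43 = 34.3 mg/kg, against 3 × 10 = 30 mg/kg.

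**If a site scaled from the example to other weights.** The implied factor is 32 / 70 = 0.457 mL/kg, against a correct 10 / 25 = 0.400 mL/kg. The ratio is again 1.143, so the excess would be 14.3% at every weight.

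**Could another reading rescue the 32 mL?**

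- Keeping 700 mg, the concentration would have to be 700 / 32 = 21.9 mg/mL. The document gives no such figure.
- Keeping 25 mg/mL and 10 mg/kg, the patient would have to weigh 32 × 25 / 10 = 80 kg. The example says 70 kg.
- The document gives no overfill or line-loss allowance, and Section 9.2 has the line flushed at the end of the infusion.
- A text-extraction fault is unlikely: the volume is written out in words, and it adds with the saline to the stated 200 mL.

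**Comparison with doses already tested.** Section 4.2.2 lists phase I doses of 2.5, 5 and 10 mg/kg weekly and 10, 15 and 20 mg/kg every two weeks. The highest of the two-weekly doses averages 20 / 2 = 10 mg/kg per week. A weekly dose of 11.43 mg/kg is above both the highest weekly dose and the highest average weekly rate on that list.

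**The case against.** The arithmetic is not in dispute. The case on the other side concerns how likely the error is to reach a patient and how much it would matter.

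1. **The Pharmacy Manual.** Section 5.2.2 refers to pharmacy manuals for the specific preparation instructions. They were not available for this review, so the working text in the pharmacy may be correct. This stands as a limit on what can be claimed. It does not remove the problem: if the manual says 28 mL, it contradicts the protocol, and if it says 32 mL, the excess is systematic.
2. **The correct rule sits in the same bullet.** A pharmacist who calculates 700 mg and divides by 25 mg/mL will draw 28 mL. The error takes effect only if someone copies the 32 mL or scales from it. This also stands, and the consequence must be stated conditionally. Nothing in the document shows that any dose was misprepared.
3. **Clinical effect is not established.** Section 4.2.2 reports no dose-limiting toxicity and no maximum tolerated dose, with single infusions up to 20 mg/kg. It also regards a fixed 700 mg dose as acceptable, and that dose already equals 11.43 mg/kg in a patient of 61.25 kg (700 / 61.25). So the document gives no ground for predicting serious harm. It equally gives no weekly experience above 10 mg/kg.
4. **Doses can be recovered.** Section 7.1.1.7 takes doses from pharmacy records and nursing notes, and Section 10.2.5.2.1 adds a drug audit for sampled patients. These would help to detect a systematic error afterwards but do not prevent one.
5. **No statistical quantity uses this figure.** The Simon two-stage design, the toxicity boundary and the endpoint definitions in Section 8.2 do not depend on it. That is correct.

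These points limit the probable harm. None of them explains the 32 mL.

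**Conclusion.** The example is wrong as written. At the stated concentration, the 32 mL draw gives 800 mg instead of 700 mg: 11.4 mg/kg, or 14.3% above the protocol dose. The document offers no explanation for the difference.

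The direction rests on 25 mg/mL being the true concentration. Its repetition in Section 9.2 and Table 7, and its agreement with 250 mg in 10 mL, make that much the likeliest reading. If the true strength were instead the 21.9 mg/mL that the 32 mL implies, the example would be right and the labelled strength wrong. A site drawing 28 mL would then give 28 × 21.875 = 612.5 mg, which is 12.5% too little. Either way, one figure in the section is wrong, and the sponsor has to establish which.

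The effect on patients and on the interpretation of results is conditional on the example having been copied or scaled. Because the protocol directs staff to follow it, and the resulting weekly dose would exceed any weekly dose listed from phase I, it must be corrected.

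**What to change.** 1. Confirm the vial concentration against the product label. If it is 25 mg/mL, change the example in Section 9.2 to 28 mL of sEphB4-HSA and 172 mL of normal saline, total 200 mL.
2. State the conversion explicitly beside the milligram formula: volume in mL = total dose in mg / 25. Staff then need not infer it from an example, and it also covers the reduced dose levels in Section 5.2.1.3.
3. Check the Pharmacy Manual for the same example, and send a short memo to every dispensing pharmacy.
4. Check dispensing and accountability records for doses prepared from the example. Use the recorded volume drawn where there is one. Vial counts help at 70 kg, where 28 mL takes three 10 mL vials and 32 mL takes four, but not at every weight. At 80 kg, for example, the correct 32 mL and the scaled 36.6 mL (80 × 0.457) both take four. If any such doses are found, report the dose actually given alongside the safety and response results.

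The cost is a correction to one bullet, a memo, and a records check. The sample size, analysis and visit schedule do not change.
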